2.1.1.3 Tivozanib Safety Experience

Excluding the phase 3 trial, safety data are summarized below for 14 completed or ongoing clinical studies of tivozanib. Adverse events were generally manageable using standard medical therapy and/or discontinuation or reduction of study drug.

Related treatment emergent adverse events (TEAEs) that resulted in a fatal outcome occurred in 4 subjects and included post-procedural hemorrhage, cerebrovascular accident, pulmonary embolism, and hypertension.

Related TEAEs for combination therapy studies can be summarized as follows:

Combination therapy studies: Related TEAEs were reported in 65/81 subjects (80.2%). The most frequently related TEAEs (occurring in \geq 10% of treated subjects) were fatique (50.6%), nausea (40.7%), diarrhea (35.8%), stomatitis (33.3%), vomiting (24.7%), decreased appetite (23.5%), hypertension (22.2%), peripheral sensor neuropathy (22.2%), epistaxis (19.8%), dysphonia (16.0%), thrombocytopenia (16.0%), alopecia (14.8%), headache (12.3%), neutropenia (12.3%), and blood triglycerides increased (11.1%).

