5. TREATMENT PLAN

Treatment will be administered on an outpatient basis. Expected toxicities and potential risks as well as dose modifications are described in Section 6 (Expected Toxicities and Dosing Delays/Dose Modification).

The treatment plan is outlined in the table below. Tivozanib will be taken orally once daily for 3 out of 4 weeks on a continuous basis. Enzalutamide will be taken orally once daily without any scheduled interruptions, on a continuous basis.

| Treatment Description | | | | | | |
|-----------------------|-------------|--------|---------------|------------|-----------------|--|
| Agent | Precautions | Dose | Route | Schedule | Cycle Length | |
| Tivozanib | None | 1.5 mg | PO once daily | Weeks 1-3 | | |
| Enzalutamide | None | 160 mg | PO once daily | Continuous | 28 days | |

Because this combination has not been previously tested, a safety run-in will be conducted at the outset of the trial. After the first 3 patients are enrolled, accrual will be held until all three patients complete the first 1 month of treatment. Additionally, after a total of 10 patients are enrolled, these patients will be analyzed for safety and toxicity by the DSMC. If any treatment-related, expected or unexpected grade 3 or higher adverse events occur during the first month of treatment in the first 3 patients, or if the rate is >30% among the first 10 patients during the first month of treatment, further accrual will be halted for reconsideration of the appropriateness of the dosing schedules.

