12.2 Safety Monitoring

The DF/HCC Data and Safety Monitoring Committee (DSMC) will review and monitor toxicity and accrual data from this trial. The committee is composed of clinical specialists with experience in oncology and who have no direct relationship with the study. Information that raises any questions about participant safety will be addressed with the Principal Investigator and study team.

The DSMC will meet quarterly and/or more often if required to review toxicity and accrual data. Information to be provided to the committee may include: up-to-date participant accrual; current dose level information; DLT information; all grade 2 or higher unexpected adverse events that have been reported; summary of all deaths occurring within 30 days for Phase I or II protocols; any response information; audit results, and a summary provided by the study team. Other information (e.g. scans, laboratory values) will be provided upon request.

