14. STATISTICAL CONSIDERATIONS

14.1. Study Design/Endpoints

The phase 2 study will evaluate the efficacy of enzalutamide and tivozanib in patients with mCRPC. The primary endpoint will be progression free survival (PFS), defined as the time from registration to the earlier of progression (radiographic or clinical) or death and, if censored, the date of last disease evaluation. Based on phase 3 data, the median PFS with enzalutamide alone in chemotherapy naive mCRPC is 14 months. The hypothesis is that the addition of tivozanib will significantly enhance efficacy. An improvement of 60% to a median PFS of 22.4 months will be considered worthy of further study. Assuming exponential distribution, this implies a hazard ratio (HR) of 0.625 relative to historical control (hazard rate from 0.0495 to 0.0309). Using a one-sample exponential test, there will be 80% power to demonstrate a 60% improvement at a one-sided Type 1 error rate of 10% with enrollment of 38 patients and 20 PFS events.

Because this combination has not been previously tested, a safety run-in will be conducted at the outset of the trial. After the first 3 patients are enrolled, accrual will be held until all three patients complete the first 1 month of treatment. Additionally, after a total of 10 patients are enrolled, these patients will be analyzed for safety and toxicity by the DSMC. If any treatment-related, expected or unexpected grade 3 or higher adverse events occur during the first month of treatment in the first 3 patients, or if the rate is >30% among the first 10 patients during the first month of treatment, further accrual will be halted for reconsideration of the appropriateness of the dosing schedules.

The table below gives the probability of observing 1 or more toxicities among the first 3 patients or 3 or more among the first 10 patients given different true underlying toxicity rates.

| True toxicity rate | 1% | 10% | 20% | 30% | 40% | 50% |
|--|--------|-------|-------|-------|-------|-------|
| Probability of Stopping Early (≥ 1/3) | 0.030 | 0.271 | 0.488 | 0.657 | 0.784 | 0.875 |
| Probability of Stopping Early (≥ 3/10) | <0.001 | 0.070 | 0.322 | 0.617 | 0.832 | 0.945 |

Thus, if the true underlying proportion of toxic events is 30% at the current dosing schedules, there is a greater than 60% chance of stopping early.

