14.3. Analysis of Secondary Endpoints

Secondary clinical endpoints will include toxicity, overall survival, time to PSA progression, objective response rate and PSA response rate.

We will monitor toxicities experienced by all treated patients on the study. With 42 patients, the maximum width of a 90% CI for a given toxicity rate is 27%. The probability of observing at least one rare severe toxicity (true rate=5%) is 88%.

Objective and PSA response will be estimated as the number of responders divided by the total number of evaluable patients. Exact binomial confidence intervals will be calculated for the true response proportion.

Distribution of overall survival defined as the time from registration to death due to any cause will be estimated using Kaplan-Meier methods. PSA progression will be defined according to the recommendations of PCWG2¹⁵.

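### Beyond month 1 of the first 10 men, no stated toxicity rate obliges a pause in accrual, even if the cumulative rate passes the sponsor's own 30% limit

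*Combined protocol and SAP*

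**What the plan says.** Sections 1.1, 5 and 14.1 carry the same trigger. Its first part is "If any treatment-related, expected or unexpected grade 3 or higher adverse events occur during the first month of treatment in the first 3 patients". Its second part is "or if the rate is >30% among the first 10 patients during the first month of treatment, further accrual will be halted", and the halt is for reconsidering the dosing schedules. Section 5 names the reviewer of the second part: "Additionally, after a total of 10 patients are enrolled, these patients will be analyzed for safety and toxicity by the DSMC".

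The table in Section 14.1 is introduced as giving the "probability of observing 1 or more toxicities among the first 3 patients or 3 or more among the first 10 patients". For a true rate of 30%, the text concludes that "there is a greater than 60% chance of stopping early".

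Section 14.2 plans 42 men at 2 per month, and Section 1.1 continues treatment until progression or unacceptable toxicity. For the period after the run-in:

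- Section 12.2: "The DSMC will meet quarterly and/or more often if required to review toxicity and accrual data". Safety questions are taken up with the Principal Investigator and study team.
- Section 14.3: "We will monitor toxicities experienced by all treated patients on the study". It then gives a confidence interval width and a detection probability, but no limit.
- Sections 5.1.2, 6.2 and 6.4 hold, interrupt or end treatment for individual men in any cycle. They do not act on accrual.
- Section 11.5 requires deaths to be reported within 24 hours to the manufacturer and NCCN, and promptly to the FDA and IRB.

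**The concern.** The plan justifies the run-in by noting that the combination is untested, and it names a month-1 rate above 30% as the point at which accrual should stop for thought. That limit is applied once, to 10 men. If the cumulative month-1 rate later rose above it, nothing in the plan would require anyone to pause. Ten men are too few to settle whether the rate is above 30%, so the limit is checked where it is least informative and then dropped.

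Treatment after month 1 is outside the trigger for every man, including the first 10. Section 2.1.1.3 gives a reason to care about serious events: "Related treatment emergent adverse events (TEAEs) that resulted in a fatal outcome occurred in 4 subjects". An acceptable tolerability profile is also a secondary objective (Section 1.3), yet no limit applies over most of the exposure.

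Continuity of data is a further weakness. The run-in counts expected and unexpected events. The adverse events that Section 12.2 itemises as possible DSMC information are unexpected ones of grade 2 or higher. Section 2.1.1.3 treats hypertension, the most frequent event with tivozanib (42.4%, all grades), as expected up to grade 3. The list is permissive and the DSMC may ask for more, but nothing ensures that the run-in statistic goes on being computed.

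**Working it through.** **Inputs.** Run-in rule, table and 30% limit: Section 14.1. Total of 42 men, 2 per month, 21 months of accrual plus 6 of follow-up: Section 14.2. Median PFS of 14 and 22.4 months: Section 14.1.

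**Step 1: reproduce the plan's table.** Exact binomial tails, P(at least 1 of 3) = 1 − (1 − p)^3 and P(at least 3 of 10), match it. The one visible difference is 0.8327 against a printed 0.832 at 40%.

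**Step 2: compare text with table.** More than 30% of 10 men means at least 4, but the table uses at least 3.

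**Step 3: probability of passing both parts.** No event in the first 3, then few enough in the next 7:

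- Text cut: (1 − p)^3 × P(Bin(7, p) ≤ 3)
- Table cut: (1 − p)^3 × P(Bin(7, p) ≤ 2)

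| True month-1 rate | 10% | 20% | 30% | 40% | 50% |
|---|---|---|---|---|---|
| Stop, ≥1/3 (plan) | 0.271 | 0.488 | 0.657 | 0.784 | 0.875 |
| Stop, ≥3/10 (plan) | 0.070 | 0.322 | 0.617 | 0.832 | 0.945 |
| Stop, ≥4/10 (text) | 0.013 | 0.121 | 0.350 | 0.618 | 0.828 |
| Pass both, text cut | 0.727 | 0.495 | 0.300 | 0.153 | 0.0625 |
| Pass both, table cut | 0.710 | 0.436 | 0.222 | 0.091 | 0.028 |

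Example at 40%, text cut: 0.6^3 = 0.216; P(Bin(7, 0.4) ≤ 3) = 0.710; product 0.153.

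The claim of more than 60% at a true 30% survives for the combined rule as worded (1 − 0.300 = 0.700), although the second part alone gives 0.350.

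**Step 4: what lies outside the trigger.** 42 − 10 = 32 men, and 32/42 = 76%. If the rule is passed, the expected number of those men with a month-1 event is 32p: 9.6, 12.8 and 16 at 30, 40 and 50%.

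For exposure, assume uniform accrual, exponential PFS and treatment until progression. Expected man-months are 42 times the average of (1 − e^(−λt))/λ over t from 6 to 27 months, with λ = ln 2/median. This gives 456 at a 14-month median and 528 at 22.4 months. The trigger looks at about 10 of these: 10/456 = 2.2%, 10/528 = 1.9%.

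**Step 5: carry the limit forward.** More than 30% of 20 is at least 7; more than 30% of 30 is at least 10. Starting from the distribution of counts among regimens that passed (text cut), add 10 men by convolution, remove paths at or above 7, add 10 more, and remove paths at or above 10.

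| True month-1 rate | 10% | 20% | 25% | 30% | 40% | 50% |
|---|---|---|---|---|---|---|
| Halted at 20 or 30 men, given run-in passed | 0.1% | 4% | 12% | 27% | 65% | 91% |

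The overall chance that a regimen with a true 40% rate goes forward unflagged falls from 0.153 to 0.153 × (1 − 0.645) = 0.054.

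**The case against.** The strongest reply is that a run-in followed by discretionary review is an accepted design that contradicts nothing in the plan. The committee has no direct relationship with the study and, at 2 men per month, meets about every 6 men, more often than looks at 20 and 30. Patient-level rules protect each man in every cycle. A fixed rate could also pause the trial over manageable hypertension: the trigger counts expected events, and Section 6.2.1 classes intensified treatment of previously controlled hypertension as Grade 3.

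Much of this stands, and it rules out three stronger readings that a reader might infer:

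- **That toxicity goes unwatched after the run-in.** Section 12.2 says otherwise. What is missing is a rate that obliges a pause, not review.
- **That a later treatment-related death would not reach the DSMC.** Section 12.2 lists a summary of deaths within 30 days among the information it may receive and allows extra meetings. What is absent is a mandatory pause.
- **That a too-toxic regimen often passes.** The joint probabilities are 15% at 40% and 6% at 50%, and lower with the table's cut. The 30% column sits at the sponsor's limit, not above it.

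The four fatal events also carry limited weight. No denominator or timing is given for them, and Section 6.1, listing the same four event types, calls one probably and three possibly related. They show neither late risk nor its size.

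The reply does not explain why a limit thought necessary at 10 men should lapse when more informative numbers become available to the same committee.

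**Conclusion.** The point holds as a gap in prespecified, trial-level triggers. For 32 of 42 men, and for all treatment after month 1, no stated rate obliges a pause in accrual, even above the sponsor's own limit. Chance passes of the run-in matter mainly at true rates of 30 to 40%: 30% and 15% as worded, 22% and 9% with the table's cut. The separate conflict between text (at least 4 of 10) and table (at least 3 of 10) must be settled first, because every later count depends on it.

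These figures assume independent men, a constant month-1 rate, and a halt counted as not passing, although the plan allows resumption after reconsideration. The exposure figures rest on the plan's accrual and PFS assumptions and ignore early stopping for toxicity.

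This is a worthwhile and inexpensive safety improvement, not a finding that the trial lacks oversight.

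**What to change.** 1. **Reconcile Section 14.1.** Make the text and the table use the same cut for the first 10 men, and carry the result into Sections 1.1 and 5.
2. **Extend the limit in Sections 12.2 and 14.1.** Have the existing DSMC apply the sponsor's own reconciled month-1 accrual limit cumulatively at later looks, for example when 20 and 30 men have completed month 1. Add the operating characteristics to the Section 14.1 table. On the more-than-30% reading the counts are 7 of 20 and 10 of 30, with the results shown above. If the table's cut is the intended one, the counts and probabilities must be redone.
3. **Cover later cycles by reporting.** With looks at 20 and 30 men, the rule still sees only about 30 man-months (30/456 = 6.6%), and men 31 to 42 (12 of 42, 29%) have no later look. State that at each review the DSMC receives cumulative related grade 3 or higher events from all cycles, expected and unexpected, and treatment-related deaths. Whether a death or late toxicity pauses accrual is for the sponsor and DSMC to decide; no such rule is proposed here.

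The cost is protocol wording and extra table rows, using the existing committee and adverse event data already collected. The real downside is unnecessary pauses among regimens that passed the run-in: about 4% at a true 20%, 12% at 25% and 27% at 30%, some of which may reflect expected hypertension. As in the run-in, a pause is for reconsideration, not termination. No dosing or patient-level rule changes.

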1.1 Study Design

We plan to conduct a single arm, open label, combination study with tivozanib and enzalutamide (enz) in men with metastatic castration resistant prostate cancer (mCRPC). All men will receive standard dosing of each drug, with tivozanib administered at 1.5 mg once daily for 3 weeks followed by a one-week break, and enzalutamide taken continuously at 160 mg once daily. Both will be orally administered. A single dose reduction of tivozanib will be permitted, if necessary, to 1.0 mg daily. Patients will continue on treatment until they experience objective or clinical disease progression, or unacceptable toxicity.

Because this combination has not been previously tested, a safety run-in will be conducted at the outset of the trial. While waiting for the first 3 patients to complete one month of treatment, no more than 10 total patients may be enrolled. These patients will be analyzed for safety and toxicity. If any treatment-related, expected or unexpected grade 3 or higher adverse events occur during the first month of treatment in the first 3 patients, or if the rate is >30% among the first 10 patients during the first month of treatment, further accrual will be halted for reconsideration of the appropriateness of the dosing schedules.

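### The Section 14.1 run-in table evaluates stopping at 3 or more of 10, but the written rule (>30%) needs 4 or more; Section 1.1 also contradicts Sections 5 and 14.1 on holding accrual after 3 patients

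*Combined protocol and SAP*

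**What the plan says.** Sections 1.1, 5 and 14.1 give the run-in stopping rule in the same terms. The first limb is "If any treatment-related, expected or unexpected grade 3 or higher adverse events occur during the first month of treatment in the first 3 patients". The second is "if the rate is >30% among the first 10 patients during the first month of treatment, further accrual will be halted", so that the dosing schedules can be reconsidered.

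Section 14.1 then introduces a table of stopping probabilities, described as the chance of observing "1 or more toxicities among the first 3 patients or 3 or more among the first 10 patients". For true toxicity rates of 1, 10, 20, 30, 40 and 50%, the row for at least 1 of 3 reads "0.030 | 0.271 | 0.488 | 0.657 | 0.784 | 0.875" and the row for at least 3 of 10 reads "<0.001 | 0.070 | 0.322 | 0.617 | 0.832 | 0.945". The section concludes that a true rate of 30% gives a better than 60% chance of stopping early.

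On accrual during the first look, Section 1.1 says: "While waiting for the first 3 patients to complete one month of treatment, no more than 10 total patients may be enrolled". Section 5 says: "After the first 3 patients are enrolled, accrual will be held until all three patients complete the first 1 month of treatment". Section 14.1 repeats the Section 5 sentence.

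**The concern.** A rate above 30% in 10 patients means 4 or more events, because 3 of 10 equals 30% and does not exceed it. The table's lead-in sentence and its row label both use 3 or more, so the protocol carries two thresholds for one decision. With exactly 3 of 10, the rule says accrual continues and the table counts the run-in as stopped.

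The two rows are also shown as separate events, although the first 3 patients are among the 10. If the first look passes with 0 of 3, the second look triggers under the written rule only when at least 4 of the next 7 have an event. No row gives the overall chance of stopping.

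The accrual instructions conflict as well. Section 1.1 allows up to 10 − 3 = 7 further men to start treatment before the first 3 have been observed for a month; Sections 5 and 14.1 allow none.

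This is the protocol's only numerical safety-stopping rule, and the combination had not been tested before. The DSMC and the IRB would take the table as a description of how well the rule protects patients.

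**Working it through.** **Inputs.** The limits of at least 1 of 3 and above 30% of 10 come from the rule in Sections 1.1, 5 and 14.1. The threshold of at least 3 of 10, the true rates and the printed probabilities come from the Section 14.1 table. The rate is taken to be the proportion of patients with a qualifying event, with independent patients and all 10 assessable.

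**Formula.** Exact binomial upper tail: P(X ≥ r | n, p) = Σ from k = r to n of C(n,k) p^k (1−p)^(n−k).

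**Step 1: reproduce the printed table.** P(X ≥ 1 | 3, p) = 1 − (1−p)³ gives 0.0297, 0.271, 0.488, 0.657, 0.784 and 0.875, which matches the first row. P(X ≥ 3 | 10, p) gives 0.0001, 0.0702, 0.3222, 0.6172, 0.8327 and 0.9453, which matches the second row (the printed 0.832 is 0.8327 cut rather than rounded). The table is therefore right for at least 3 of 10.

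**Step 2: apply the written rule, at least 4 of 10.** At p = 0.30, P(X = 3 | 10) = 120 × 0.3³ × 0.7⁷ = 0.2668, so P(X ≥ 4) = 0.6172 − 0.2668 = 0.3504.

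| True rate | Printed (≥3/10) | Written rule (≥4/10) | Overstatement |
|---|---|---|---|
| 1% | <0.001 | <0.001 | none at this precision |
| 10% | 0.070 | 0.013 | 0.057 |
| 20% | 0.322 | 0.121 | 0.201 |
| 30% | 0.617 | 0.350 | 0.267 |
| 40% | 0.832 | 0.618 | 0.215 |
| 50% | 0.945 | 0.828 | 0.117 |

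(Differences are taken from unrounded values.)

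**Step 3: combine the two looks.** A run-in that passes the first look has 0 of 3, so

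P(stop at either look) = [1 − (1−p)³] + (1−p)³ × P(X ≥ k | 7, p),

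with k = 4 for the written rule and k = 3 for the table's threshold. At p = 0.30 and k = 4: 0.657 + 0.343 × 0.126 = 0.700.

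| True rate | Second look triggers after 0/3 (≥4 of 7) | Overall, ≥1/3 then ≥4/10 | Overall, ≥1/3 then ≥3/10 | Difference in overall |
|---|---|---|---|---|
| 1% | <0.001 | 0.030 | 0.030 | <0.001 |
| 10% | 0.003 | 0.273 | 0.290 | 0.017 |
| 20% | 0.033 | 0.505 | 0.564 | 0.059 |
| 30% | 0.126 | 0.700 | 0.778 | 0.078 |
| 40% | 0.290 | 0.847 | 0.909 | 0.063 |
| 50% | 0.500 | 0.938 | 0.972 | 0.034 |

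The last column is the probability of 0 of 3 followed by exactly 3 of 7, which is 35 p³ (1−p)⁷. It is largest at p = 0.30: 35 × 0.027 × 0.0824 = 0.078.

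**Step 4: check the concluding sentence.** At a 30% true rate the 10-patient look alone stops with probability 0.350, not above 0.60. The 3-patient look alone gives 0.657 and the two together 0.700, so the sentence holds only through the first look.

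**Step 5: compare the accrual instructions.** Section 1.1 sets a ceiling of 10 enrolled during the first month of observation; Sections 5 and 14.1 set it at 3. Both cannot be followed.

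**The case against.** The strongest reply is that the run-in is a two-look procedure and should be judged as one. For the written rule the overall probabilities (0.273, 0.505, 0.700 and 0.847 at 10 to 40%) exceed both printed rows at each of those rates; only at 50% is the overall figure lower than a printed one (0.938 against 0.945). The 3-patient row is exact and the concluding sentence remains true. The choice between 3 and 4 matters only after 0 of 3 and then exactly 3 of 7, at most 7.8% of run-ins. All of this stands, and it limits the practical loss of protection. It does not make the 10-patient row correct for the rule it is meant to describe.

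The DSMC also reviews the first 10 patients whatever the count, and meets at least quarterly. That helps, but the committee would still hold a rule and a table that disagree at 3 of 10. A halt is for reconsideration, so accrual might resume after an event in the first 3; the figures conditional on 0 of 3 then do not cover every course the run-in can take.

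On accrual, 7 further men is a ceiling. At the 2 patients per month planned in Section 14.2, about 2 would be expected during the third patient's month. The contradiction remains.

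Finally, the protocol version is dated 11.19.2020 and has a separate visit schedule from Cycle 46, which suggests that the run-in may be over. The documents do not say so. If it is, the correction bears on reporting rather than conduct.

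**Conclusion.** The point holds on both parts. The 10-patient row belongs to a different threshold from the rule in Sections 1.1, 5 and 14.1, and overstates that rule's stopping probability by 0.057 to 0.267 for true rates from 10 to 50%, most at 30%. The overstatement is confined to that row. Across both looks the effect of the threshold is at most 0.078. Section 1.1 separately contradicts Sections 5 and 14.1 on whether accrual is held after 3 patients.

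The figures assume that the rate counts patients with an event, that patients are independent and that all 10 are assessable. The overall figures also treat a halt at the first look as stopping. The documents do not show which threshold or which accrual instruction is intended. Because this is the only numerical safety rule for an untested combination, the inconsistency has to be resolved even though the effect across both looks is modest.

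**What to change.** The sponsor should decide which threshold is intended and make text and table describe it.

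- If the >30% wording is kept, relabel the second row as at least 4 of 10, change the lead-in sentence to match, and print <0.001, 0.013, 0.121, 0.350, 0.618 and 0.828.
- If 3 or more of 10 is intended, keep the row and reword the rule in Sections 1.1, 5 and 14.1.
- In either case, add a row for the overall probability of stopping: 0.030, 0.273, 0.505, 0.700, 0.847 and 0.938 with at least 4 of 10, or 0.030, 0.290, 0.564, 0.778, 0.909 and 0.972 with at least 3 of 10. Tie the concluding sentence to that row, and state that the rate counts patients with an event.
- Reconcile the accrual sentence in Section 1.1 with Sections 5 and 14.1; the choice is the sponsor's.
- If the run-in has been completed, report which threshold and which accrual instruction were applied.

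The cost is wording and a small table change. If the >30% rule is kept, the stated probabilities for the 10-patient look become less favourable.
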